## 3.5 Pharmacokinetic and Pharmacodynamic Marker Analysis

### 3.5.1 Data Assembly

The concentration data of CCX140 as reported by the respective bioanalytical group will be used without rounding for all analysis.

Subjects with major protocol deviation such as PK deviation or compliance issues may be excluded from the PK analyses (i.e. descriptive statistics) upon agreement with the Sponsor on case by case basis but all data will be listed. Values that are excluded from the analysis will be footnoted appropriately.

The following general rules should apply for handling missing data or concentration below the lower limit of quantification (BLQ) on Day 1:

- All BLQs will be set to “0” for Day 1 visit.
- If the BLQ occurs between 2 quantifiable drug concentrations within a full PK profile for Day 1 visit, the BLQ is excluded from all PK assessments.
- Missing pre-dose concentrations on Day 1 will be set as “0” and included in PK evaluation
- Missing post-dose values on Day 1 will not be imputed and will be excluded from PK evaluation
- Values that are excluded from the analysis will be documented appropriately.
- Pre-dose values on Day 1 that are greater than 5% of  $C_{max}$  will be documented. A sensitivity analysis (with inclusion and exclusion of the subjects with the pre-dose concentration  $>5\%$  of  $C_{max}$ ) will be presented and documented in the study report.

The following general rules should apply for handling missing or BLQ data on Day 15:

- If the BLQ occurs between 2 quantifiable drug concentrations within a full PK profile for Day 15 visit, the BLQ is excluded from all PK assessments.
- Missing pre-dose concentrations on Day 15 will be not imputed and excluded from PK evaluation. In case of missing pre-dose concentration on Day 15, AUCs on Day 15 will not be calculated for this subject.
- Missing post-dose values on Day 15 will not be imputed and will be excluded from PK evaluation
- Values that are excluded from the analysis will be documented appropriately.

The sample time of the pre-dose samples on Day 1 and Day 15 will be uniformly considered as

time “0”.

For the trough concentration for post-Day 1 visits and at 2 days, 7 days and 14 days after the last dose of study drug, all missing or BLQ concentration will not be imputed and will be excluded from the descriptive summary.

For Day 1 and Day 15 visits, individual PK plots or individual PK parameters, since there is no collection window specified for post-dose PK sampling, will be based on actual times recorded. For concentration versus time descriptive statistical summaries and mean plot preparation, nominal time points will be used. If the difference of post-dose sampling time is  $> 5$  minutes from the nominal sampling times for time points  $< 2$  hours or  $> 5\%$  for time points  $\geq 2$  hours, the corresponding concentration data will be excluded from the concentration summary and mean plot preparation, but will still be used in the individual plots and the calculation of PK parameter.

For Day 1 and Day 15 visits, if the pre-dose PK sample is collected after dosing, the corresponding concentration will be treated as a post-dose value and will be used for individual plotting and PK parameter calculation.

CCX140 plasma concentration results will be used to calculate trough plasma concentrations ( $C_{min}$ ) over the course of the clinical trial.

For post-Day 1 visits, the allowable time window for PK trough sampling is  $\pm 3$  hours (i.e. 25% of dosing interval of 12 hours) for 10 or 15 mg BID dosing groups (C and D), and  $\pm 6$  hours (i.e. 25% of dosing interval of 24 hours) for 5 mg QD dosing group (B) in the blinded treatment study phase (up to Week 12). However, in the open label extension phase (Week 13 to Week 24), all subjects will be given 15 mg BID, therefore, the allowable time window for PK trough sampling is  $\pm 3$  hours for all subjects. If the exact time (measured from dosing) is outside of the collection window, the corresponding concentration will be excluded from trough concentration versus time descriptive statistical summaries and median plot preparation, but will still be used in the individual plots.

For the PK blood samples collected at 2 days, 7 days and 14 days following the last dose of study drug, as well at the Follow-up Visit, the actual sampling time should not exceed 5% of the nominal sampling time. If the exact time (measured from dosing) is outside of the collection window, the corresponding concentration will be excluded from concentration versus time descriptive statistical summaries and median plot preparation, but will still be used in the individual plots.

Non-numerical readouts except BLQ [e.g. NA (not available) or NRE (not reliable)] will be set as missing and will not be included in the PK evaluation.

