All subjects will take blinded study medication in the morning and evening, with or without food, for 84 consecutive days. Following the 84-day blinded dosing period, all subjects will take open label CCX140-B for an additional 84 days at the highest dose under evaluation, currently planned to be 15 mg twice daily. If the Sponsor, with the advice of the unblinded Data Monitoring Committee (DMC), determines that 15 mg twice daily exceeds the maximum tolerated dose, then the dose administered during the open label period will be adjusted downward from the planned dose to the highest dose that is still under evaluation. There will be a 28-day follow-up period after completion of treatment.

During the treatment period, eligible subjects will visit the study center on Study Days 1, 8, 15, 29 (Week 4), and Weeks 8, 12 (primary endpoint), 13, 16, 20, and 24 for study procedures including interval history, physical examination and vital signs, ECG, study questionnaires, and collection of blood and urine. Subjects will discontinue study drug as of Study Day 169 (Week 24), and will return for a follow up visit on Week 28. When feasible, upon discontinuation of treatment for any reason a sample of whole blood should be collected for assessment of elimination 2, 7 and 14 days after the final dose of CCX140-B (or placebo).

For assessment of adverse events of special interest, study procedures will include

- Complete blood count with differential, morphology assessment, reticulocyte count, hemoglobin, LDH and total and direct bilirubin, to assess early evidence of hemolysis;
- The AIDS Clinical Trials Group Brief Peripheral Neuropathy Screening Tool (ACTG-BPNST), to assess early evidence of neuropathy;
- Monitoring for adverse events of infection;
- Alkaline phosphatase, ALT, AST and total and direct bilirubin; to assess for evidence of drug induced liver injury.

For assessment of pharmacokinetics, study procedures will include

- **Seven** blood samples collected over 6 hours on Study Day 1 and Study Day 15 to assess AUC₀₋₆ following the first administration of study drug, and at steady state;
- Assessment of C_{min} at intervals to ensure that exposure is within the projected range, with adequate safety margin based on the NOAEL established in preclinical toxicology;
- Upon discontinuation of treatment for any reason, collection of blood at 2 days, 7, days and 14 days following discontinuation to assess elimination kinetics.

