| CCX140-B Open label dispensing | | | | | | | X | | X | X | | | | |
| CCX140-B Open label dosing ⁶ | | | | | | | X → | → | → | → | → | | | |
| CCX140-B accountability | | | X | X | X | X | X | X | X | X | X | | | |
| Plasma MCP-1 | | X ³ | X | X | X | | X | X | X | | X | X | | |
| PD plasma/serum sample collection | | X ³ | X | X | X | | X | X | X | | X | X | | |
| Urine MCP1-1, MCP-1/Creatinine | | X ³ | X | X | X | | X | X | X | | X | X | | |
| PD urine sample collection | | X ³ | X | X | X | | X | X | X | | X | X | | |
| PK plasma sample collection | | X ^{3,5} | X | X ⁵ | X | X | X | X | X | X | X | X ¹¹ | X ¹¹ | |

| Assessments | Screening | Double-Blind Treatment ¹ | | | | | | | Open-Label Treatment | | | | Follow-Up | Variable |
|--------------------------|-----------------|-------------------------------------|---|----|----|----|-----------------|----|----------------------|-----|-----|------------------------|-------------------------------|-------------|
| | | Initial Study Phase | | | | | | | Extension Phase | | | | | Elimination |
| Days | ≤ 28 days | 1 | 8 | 15 | 29 | 57 | 85 ⁷ | 92 | 113 | 141 | 170 | 113 ⁷ & 198 | 2,7 & 14 days post final dose | |
| Weeks | ≤ 4 weeks | | 1 | 2 | 4 | 8 | 12 ⁷ | 13 | 16 | 20 | 24 | 16 ⁷ & 28 | | |
| Concomitant medications | X ¹⁰ | X | X | X | X | X | X | X | X | X | X | X | | |
| Adverse event assessment | | X | X | X | X | X | X | X | X | X | X | X | | |

¹Week 1 and 2 visits must occur with a ± 1 day window. Week 4 through Week 28 visits may occur within a ± 3 day window.

²Physical examination will include body weight measurements. Height will only be measured at Screening. Full physical examination will be performed at Screening and Day 1. At all other visits, limited, physical examination will be performed directed by review of systems, laboratory findings and Investigator discretion.

³These procedures must be performed before taking the first dose of CCX140-B on Day 1; in addition, CBC and bilirubin will be assessed at 2 and 6 hours following dosing in blood to be drawn at the same time as the PK sample

⁴TB screening by Interferon γ release assay (IGRA) done within 6 weeks prior to Screening or done during Screening.

⁵PK blood sample will be collected on Days 1 and 15 prior to the morning dose (time 0), and at 0.5, 1, 2, 3, 4, and 6 hours following dosing. PK samples at all other visits will be collected at time 0 only, just prior to administration of the first daily dose.

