4. STUDY DESIGN

This study will evaluate the efficacy, safety, tolerability, and pharmacokinetics of up to 12 weeks of treatment with each of three dose regimens of CCX140-B or placebo, when used in combination with stable standard of care therapy in subjects with FSGS with significant proteinuria, assessed as $UPCR \geq 1g/g$ at Screening. Following the 12-week blinded treatment period, **the study will evaluate up to 24 weeks of treatment with CCX140-B: all subjects who remain eligible** will receive active treatment for an additional 12 weeks to assess safety and durability of effect.

The target is to enroll 40 male or female subjects in this randomized, double-blind, placebo-controlled, Phase 2 study. Randomization will be stratified by **UPCR <3.5 g protein/g creatinine versus UPCR ≥3.5 g protein/g creatinine at baseline using the screening UPCR** and by the use of glucocorticoids and/or immunosuppressive medications (yes, no).

Subjects will be randomized 1:1:1:1 to one of four treatment groups:

- Group A: Placebo (N=10)
- Group B: CCX140-B 5 mg once daily (N=10)
- Group C: CCX140-B 10 mg twice daily (N=10)
- Group D: CCX140-B 15 mg twice daily (N=10)

Study medication will be taken by the subjects for 84 days, as follows:

- Group A: Three placebo tablets, taken twice daily;
- Group B: One 5 mg CCX140-B tablet and two placebo tablets in the morning; three placebo tablets in the evening;
- Group C: Two 5 mg CCX140-B tablets and one placebo tablet, taken twice daily
- Group D: Three 5 mg CCX140-B tablets, taken twice daily

All subjects will take blinded **oral** study medication **twice daily, 3 tablets** in the morning and **3 tablets in the evening**, with or without food, for **12 weeks** (84 consecutive days). Following the 84-day blinded dosing period, all subjects **who remain eligible** will take open label CCX140-B for an additional **12 weeks** (84 consecutive days) at the highest **tolerated** dose under evaluation, currently planned to be 15 mg twice daily. **The decision on the dose for the open-label period will be made** by the Sponsor, with the advice of the unblinded Data Monitoring Committee (DMC). **After completion of treatment for whatever reason, including early termination**, all subjects are expected to return at 2, 7 and 14 days after taking the last dose of study medication **for assessment of elimination phase PK and 28 days after taking the last dose of study medication for PK and safety monitoring**.

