7.13. PK Elimination Visits

Upon discontinuation of treatment for any reason, **including end of study**, a sample of whole blood should be collected for assessment of elimination at 2, 7 and 14 days after discontinuation. Record the time of blood collection.

After all study procedures have been completed, the subject will be discharged from the study. The subject's condition will be evaluated by the Investigator at the end of the clinical trial (Week 28) and appropriate standard of care medical treatment **should be implemented for** all subjects as needed.

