### 3.5.3 Pharmacokinetic Parameter

For subjects with serial samples collected (pre-dose and at 0.5, 1, 2, 3, 4, and 6 hour post-dose after the first CCX140-B dose on Day 1 and on Day 15),  $C_{max}$ ,  $T_{max}$ , and  $AUC_{0-6}$  will be determined based on individual CCX140 plasma concentration data.  $AUC_{0-12}$  or  $AUC_{0-24}$  will be determined for Day 15 assuming pre-dose level being the same as the concentration at the end of the dosing interval.

Parameters	Description
$C_{\max}$	Maximum drug concentration after the first dose; observed directly from the data. If not unique, then the first maximum concentration is used
$T_{\max}$	Time to $C_{\max}$
$AUC_{0-6}$	Area under the concentration-time curve (AUC) from time 0 to 6 hours post-dose. For 6 hours post-dose sample, the corresponding observed concentrations will be used for AUC calculation if the difference of the actual time point is <5% from the nominal time point; otherwise, the concentration at the nominal 6-hour time point will be predicted and then used for the AUC calculation.
$AUC_{0-12}$	AUC from time 0 to 12 hours post-dose on Day 15 only following 10 or 15 mg BID dosing (Groups C and D). The concentration at 12-hour time point will be assumed to be the same as the pre-dose level.
$AUC_{0-24}$	AUC from time 0 to 24 hours post-dose on Day 15 only following 5 mg QD dosing (Group B). The concentration at 24-hour time point will be assumed to be the same as the pre-dose level.

PK parameter calculations will be based on all seven continuous time points from Day 1 and Day 15 (including Time 0). The PK parameters of those subjects with less than seven continuous time points are listed as NA.

Plasma PK parameters will be calculated by standard non-compartmental analysis. The actual collection times will be used for PK parameter calculation. The linear trapezoidal rule method (equivalent to the Linear Trapezoidal Linear Interpolation in WinNonlin® Professional) will be used in the computation of AUCs.

PK parameters will be listed and summarized by treatment descriptively.

The relationship between PK parameters and renal function based on eGFR, UPCR and UACR change of UPCR or UACR from baseline, and serum albumin will be evaluated through an exploratory analysis and summarized in a separate report.

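### Blood is drawn after the last dose to assess elimination, but the SAP derives no elimination parameter, and its 5% timing rule is narrower than the protocol's window for the 28-day follow-up sample

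*SAP*

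**What the plan says.** The PK profile is a secondary objective in both documents. The Protocol Synopsis (Methodology) describes the 2-, 7- and 14-day draws as blood collected "following discontinuation to assess elimination kinetics". Protocol 7.13 repeats the request: "a sample of whole blood should be collected for assessment of elimination at 2, 7 and 14 days after discontinuation". It then adds "Record the time of blood collection", but gives no tolerance around the three days. Protocol 4 adds a sample "28 days after taking the last dose of study medication for PK and safety monitoring".

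The only visit window that reaches any of these samples is footnote 1 of the Protocol Time and Events Table: "Week 4 through Week 28 visits may occur within a ± 3 day window". Protocol 7.12 repeats ±3 days for the follow-up visit (Week 16 or Week 28). The 2-, 7- and 14-day draws sit in a separate elimination column of that table.

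For all four post-dose samples, SAP 3.5.1 says that "the actual sampling time should not exceed 5% of the nominal sampling time". A sample outside the limit is "excluded from concentration versus time descriptive statistical summaries and median plot preparation, but will still be used in the individual plots". The same section leaves missing values and values below the limit of quantification (BLQ) at 2, 7 and 14 days out of the descriptive summary. SAP 3.5.2 plans listings, individual linear and semi-logarithmic plots on actual times, and summaries and mean plots at nominal times. SAP 3.5.3 limits derived parameters to Cmax, Tmax and AUCs from the Day 1 and Day 15 profiles.

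**The concern.** Every subject who stops treatment is asked back for three extra blood draws whose stated purpose is elimination, yet the plan contains no number that describes it. This matters more than usual here. Protocol 6.4 expects loss of albumin-bound drug through proteinuria, and reports exposure about 30% lower in diabetic nephropathy subjects with albuminuria above 1 gram.

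The planned nominal-time means are a weak substitute for a half-life, for three reasons:

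- Leaving out BLQ values keeps only the higher concentrations at late times. If any occur, the mean curve flattens and elimination looks slower than it is.
- SAP 3.5.2 groups these samples by blinded-phase treatment, although subjects who completed the open-label phase were last taking the open-label dose.
- The 5% rule can remove a follow-up sample from the summary although the site kept to the protocol.

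**Working it through.** **1. Is any elimination parameter planned?**

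- The protocol's parameter lists (Synopsis, 8.3, 9.3.7) and SAP 2.3.4 give Cmax, Tmax, AUC0-6 and trough concentrations. SAP 3.5.3 adds AUC0-12 and AUC0-24 on Day 15.
- None gives a half-life, terminal rate constant or clearance. The protocol has a half-life symbol in its abbreviation list only.
- For Day 1 and Day 15, SAP 3.5.1 keeps badly timed samples in the parameter calculation. For the elimination samples there is no parameter for them to enter.

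**2. What does 5% mean in hours?** I read the rule as a limit on the deviation from nominal time. The SAP does not convert it, but it does convert its trough windows, which serve as a check on the method: 0.25 × 12 h = 3 h and 0.25 × 24 h = 6 h, both as stated. Applying 0.05 in the same way:

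| Nominal time | 5% limit | Protocol window |
|---|---|---|
| 2 days (48 h) | ±2.4 h | none stated |
| 7 days (168 h) | ±8.4 h | none stated |
| 14 days (336 h) | ±16.8 h | none stated |
| 28 days (672 h) | ±33.6 h = ±1.4 days | ±3 days |

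**3. How large is the conflict at follow-up?** Three days is 3/28 = 10.7% of nominal, about twice the SAP tolerance. Of the whole-day offsets −3 to +3, those beyond 1.4 days are −3, −2, +2 and +3: 4 of 7 (57%). If timing were continuous and uniform over ±3 days, the share outside would be 1 − 1.4/3 = 53%. Both shares assume an even spread, which the documents do not give.

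**4. Could the samples support a slope?** The half-life is not stated. Protocol 6.4 projects about 6500 ng/mL at peak and 5500 ng/mL at trough for 15 mg twice daily in people without proteinuria. Assuming log-linear decline and a Tmax of 0 to 3 h:

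- Half-life = (12 − Tmax) × ln 2 / ln(6500/5500), which is 49.8 h at Tmax 0 and 37.3 h at Tmax 3 h.
- The 2- to 14-day draws then run from 48/49.8 = 1.0 to 336/37.3 = 9.0 half-lives, a usable range where values are quantifiable.
- The 28-day sample lies at 672/49.8 = 13.5 to 672/37.3 = 18.0 half-lives. Starting from 5500 ng/mL, that leaves roughly 0.5 to 0.02 ng/mL. The assay limit is not stated, but this sample adds least.

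**The case against.** The strongest reply is that the SAP carries out the protocol's own parameter list, on which half-life never appears. Most of the protocol's references to these draws speak simply of assessing elimination, and semi-logarithmic plots on actual time do address that. Protocol 9 also assigns PK reports to designated teams, and a half-life may be planned there. This stands in part: the SAP does not depart from a listed endpoint, and the separate report cannot be checked. But the only separate report that the SAP itself describes relates PK parameters to renal function and serum albumin.

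A second reply is that a tight window is right for nominal-time means. For the early draws that is correct. On the half-lives above, a 72-hour shift changes concentration by a factor of 2^(72/49.8) = 2.7 to 2^(72/37.3) = 3.8. A ±3-day window around a 2-day sample would run from −1 to 5 days, which makes no sense.

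A reader might also infer more than the documents support:

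- **That compliant 2-, 7- and 14-day samples are dropped.** The ±3-day window is not stated for those draws, so no conflict is shown there.
- **That a 2-day draw would usually miss ±2.4 h because the last dose was in the evening.** At Weeks 12 and 24, subjects who have not yet taken the morning dose take it at the visit (Protocol 7.7 and 7.11), so a completer's last dose is normally a morning dose at the clinic.
- **That variation in the Week 24 visit adds to that of the follow-up visit.** Section 7.12 does give study-day numbers, but Protocol 4 counts the follow-up from the last dose.
- **That samples are discarded.** Excluded values stay in the listings and in the actual-time individual plots.

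**Conclusion.** Two limited points hold. First, neither document plans a terminal rate constant or half-life, although the draws are justified by elimination and belong to a secondary PK objective. Second, at the 28-day follow-up the SAP's ±1.4 days is narrower than the protocol's ±3 days, so a compliant visit 2 or 3 days off target leaves the summary: 4 of 7 whole-day offsets, assuming an even spread.

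The first point matters more. The second concerns the least informative sample and costs a place in a summary table, not the data. Neither touches the primary endpoint or a listed PK parameter, so this is an inexpensive improvement and not a correction of an error in the main analysis. It cannot be concluded that elimination will never be estimated, since the PK report was not supplied.

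**What to change.** - **SAP 3.5.3:** add a per-subject terminal rate constant and half-life, by log-linear regression on actual time since the last active dose. Include subjects with at least 3 quantifiable post-last-dose samples and make no exclusion for timing. Report how many subjects qualify in each group.
- **Last active dose:** take its date and time from the diary or visit record. In the 5 mg once-daily group the evening tablets are placebo, so a subject who stops during the blinded phase had the last active dose in the morning.
- **SAP 3.5.1:** set the follow-up summary window to the protocol's ±3 days. Leave the tighter limits for the 2-, 7- and 14-day nominal-time summaries.

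The cost is SAP wording and a standard non-compartmental output from samples already drawn. There are three downsides. The analysis grows a little. The follow-up mean carries more timing spread, although at very low expected concentrations. Some subjects will have too few quantifiable samples for a slope; these will tend to be those who clear the drug fastest, which is why the number contributing should be shown. If the separate PK report already plans this, a cross-reference in the SAP is enough for the first item.

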### 3.5.2 Pharmacokinetic Concentration

The individual plasma concentration of CCX140 will be listed.

For subjects with serial samples collected (pre-dose and at 0.5, 1, 2, 3, 4, and 6 hour post-dose after the CCX140-B dose on Day 1 and on Day 15):

- Individual plasma concentrations of CCX140 will be plotted on a linear and semi-logarithmic scale against actual sampling time points;
- Concentration data will be summarized by treatment at each nominal time point descriptively;

- Mean ( $\pm$ SD) plasma concentrations of CCX140 will be plotted on a linear and semi-logarithmic scale against nominal time points by treatment.

For subjects with pre-dose sample collected (Post-Day 1 visits):

- Individual plasma concentrations of CCX140 will be plotted by treatment on a linear and semi-logarithmic scale against visits;
- Trough concentration data, within allowable time windows, will be summarized by treatment at each visit descriptively.
- In addition, median trough concentrations ( $C_{min}$ ) of CCX140 will be plotted overlaid with the scatter plot of individual trough concentrations by treatment on a linear and semi-logarithmic scale against visits.
- The average steady state trough concentration of CCX140 for each individual subject will be calculated for a to-be-defined steady-state time period (each subject needs to have at least 3 time points in this steady state period for the calculation). The global average steady state trough concentration of CCX140 will be listed and summarized descriptively by treatment. Box and whisker plots will be prepared by treatment for comparison.

For subjects with samples collected at 2 days, 7 days and 14 days following the last dose of study drug, as well at the Follow-up Visit:

- Individual plasma concentrations of CCX140 will be plotted on a linear and semi-logarithmic scale against actual sampling time points by the treatment in blinded phase;
- Concentration data will be summarized by the treatment in blinded phase at each nominal time point descriptively;
- Mean ( $\pm$ SD) plasma concentrations of CCX140 will be plotted on a linear and semi-logarithmic scale against nominal time points by the treatment in blinded phase.

